13.1 Visit Assessments and Procedures Flow – Baseline (Visit 2)

Abbreviations: AE, adverse event; CGI-C, Clinical Global Impression of Change; C-SSRS, Columbia-Suicide Severity Rating Scale; ECG, electrocardiogram; L-DOPA, 3,4-dihydroxyphenylalanine; max, maximum; min, minute; PD, Parkinson's disease; QUIP-RS, Questionnaire for Impulsive Compulsive Disorders in Parkinson's Disease Rating Scale; UDysRS, Unified Dyskinesia Rating Scale; UPDRS, Unified Parkinson's Disease Rating Scale.

13.2 Visit Assessments and Procedures Flow – Visit 3 – Visit 7

Abbreviations: AE, adverse event; CGI-C, Clinical Global Impression of Change; C-SSRS, Columbia-Suicide Severity Rating Scale; ECG, electrocardiogram; L-DOPA, 3,4-dihydroxyphenylalanine; lab, laboratory; max, maximum; min, minute; PD, Parkinson's disease; PGI-C, Patient Global Impression of Change; PK, pharmacokinetic; QUIP-RS, Questionnaire for Impulsive Compulsive Disorders in Parkinson's Disease Rating Scale; UDysRS, Unified Dyskinesia Rating Scale; UPDRS, Unified Parkinson's Disease Rating Scale; V, visit.

## 1 Abbreviations

Term	Description
AE	Adverse Event
AIMS	Abnormal Involuntary Movement Scale
ATC	Anatomical Therapeutic Chemical
BID	Twice daily
BP	Blood Pressure
CGI-C	Clinical Global Impression of Change
CI	Confidence Interval
COVID-19	Coronavirus disease 2019
C-SSRS	Columbia-Suicide Severity Rating Scale
DSMB	Data Safety Monitoring Board
ET	Early Termination
ITT	Intention-To-Treat
LID	Levodopa-Induced Dyskinesia
LS	Least Square
MAR	Missing At Random
MCMC	Markov Chain Monte Carlo
MedDRA	Medical Dictionary for Regulatory Activities
MI	Multiple Imputation
mITT	Modified Intention-To-Treat
MMRM	Mixed Model for Repeated Measures
MMSE	Mini-Mental State Examination
NMSS	Non-Motor Symptom Scale
PD	Parkinson's Disease
PDQ-39	39-item Parkinson's Disease Questionnaire
PDSS-2	Parkinson's Disease Sleep Scale
PGI-C	Patient Global Impression of Change
PK	Pharmacokinetic

## Statistical Analysis Plan

---

PT	Preferred Term
QD	Once daily
QUIP-RS	Questionnaire for Impulsive-Compulsive Disorders in Parkinson's Disease Rating Scale
SAE	Serious Adverse Event
SAP	Statistical Analysis Plan
SI	International System of Units
SOC	System Organ Class
TEAE	Treatment-Emergent Adverse Event
UDysRS	Unified Dyskinesia Rating Scale
UPDRS	Unified Parkinson's Disease Rating Scale
WHO-DD	World Health Organization Drug Dictionary

## 2 Introduction

This Statistical Analysis Plan (SAP) describes the planned statistical analysis, shortly after the decision to terminate the study due to coronavirus disease 2019 (COVID-19) pandemic and other reasons. The SAP will serve as a complement to the study protocol and supersedes it in case of differences. The study is still ongoing, and this SAP is being finalized prior to locking the database and unblinding the study.

## 3 Study Objectives

The objectives of the study as indicated in the protocol are described below. Since the study is being terminated early, there may not be a sufficient number of subjects within each treatment arm. Therefore, the objectives may also include evaluation of only pridopidine 100 mg BID dose at the end of titration at Week 3/5 (Visit 3), the pooled active doses (pridopidine 100 mg BID and 150 mg BID) at Week 8/10 (Visit 5) and potentially comparing results with placebo data from historical data.

Study weeks are further explained in Section **Error! Reference source not found.**

### 3.1 Primary Objective

The primary objective of this study is to evaluate the efficacy of 2 dosages of pridopidine administered twice daily (BID), 100 mg BID and 150 mg BID (individually and combined) vs placebo BID for the treatment of levodopa-induced dyskinesia (LID) in subjects with Parkinson's disease (PD) at Week 8/10 (Visit 5).

The primary objective will also evaluate subjects on 100 mg BID as compared to placebo at Week 3/5(Visit 3), since both 100 mg BID and 150 mg BID groups are on 100 mg BID at the end of titration.

### 3.2 Secondary Objectives

1. To determine if the effect of pridopidine (100 mg BID, 150 mg BID and pooled 100+150 mg BID) vs placebo is associated with changes (worsening or improvement) in parkinsonian features at Weeks 3/5 and 8/10 (Visits 3 and 5).
2. To evaluate the effect of pridopidine (100 mg BID, 150 mg BID and pooled 100+150 mg BID) vs placebo on measures of global improvement, activities of daily living, and quality of life in subjects with PD LID at Weeks 3/5 and 8/10 (Visits 3 and 5).

### 3.3 Safety Objective

To evaluate the safety and tolerability of 2 dosages of pridopidine (100 mg BID and 150 mg BID) vs placebo in patients with PD LID.

### 3.4 Pharmacokinetic (PK) Objectives:

1. To evaluate the PK of pridopidine and its main metabolite TV-45065 in subjects with PD-LID

## Statistical Analysis Plan

2. To explore the relationship between pridopidine exposure and dyskinesia

### 4 Design and Type of the Study

The study was originally designed as a 16-week study with a 2 week titration phase (January 24th, 2019 original protocol, v1.1) and was modified on 15th October 2019 (Amendment 1) via Safety Urgent Measures letter to increase the titration period from 2 to 4 weeks. This change along with other changes were implemented in Amendment 1 (19th November 2019, v2.0). The duration of the study was thus increased from 16 to 18 weeks.

The study was designed as a Phase 2b, multicenter, randomized, double-blind, placebo-controlled, three-arm, parallel-group study to evaluate the efficacy, safety, and PK of pridopidine 100 mg BID and 150 mg BID vs placebo for the treatment of PD LID.

Due to COVID-19 the study was terminated early and is now considered a Phase 2 proof of concept (PoC) study. The study will evaluate efficacy and safety of the two doses of pridopidine vs placebo as well as the pooled active doses vs. placebo.

#### 4.1 Visit Structure

Study visits in the original and Amendment 1 (amended as per the Oct 15th Safety letter) are as below:

Prilenia Therapeutics

Pridopidine

Protocol: PL101-LID201 Final/1.1

24 Jan 2019

**S-Figure 1**

**Study Design**

Study week	~ 3 weeks	Up titration		Maintenance												Down titration	
		Wk 1	Wk 2	Wk 3	Wk 4	Wk 5	Wk 6	Wk 7	Wk 8	Wk 9	Wk 10	Wk 11	Wk 12	Wk 13	Wk 14	Wk 15	Wk 16
Visit (V) #	V1 screening			V3		V4			V5			V6			V7		V8 SFU
Study day	-21 to 0	1		15		29			56			77			98		112
Visit measures	Screening	Safety		Safety		Safety			Safety			Safety			Safety		Safety
		*Efficacy		Efficacy		Efficacy			Efficacy			Efficacy			Efficacy		
		*UDysRS only		PK								PK			PK		

Arms:	Placebo	Placebo												2 days 75 mg BID + 2 days 75 QD		
	Active arm 100 mg BID	100 mg BID (200mg/day) 13 Weeks														
	Active arm 150 mg BID	150mg BID (300mg/day) 12 Weeks														
Telephone contacts will be done also on Wk 1-D3, Wk 1-D7, Wk 15-D2 and Wk 15-D4 to remind up/down titration																

Abbreviations: BID, twice daily; PK, pharmacokinetic; QD, once daily; SFU, safety follow-up; UDysRS, Unified Dyskinesia Rating Scale; V, visit; Wk, week

# Statistical Analysis Plan

Prilenia Therapeutics

Pridopidine

Protocol: PL101-LID201 Protocol Amendment 1/v2.

19 Nov 2019

## Figure 1 Study Design

Study week	3-9 weeks				Maintenance												Down titration	
	Up titration				Wk 5	Wk 6	Wk 7	Wk 8	Wk 9	Wk 10	Wk 11	Wk 12	Wk 13	Wk 14	Wk 15	Wk 16	Wk 17	Wk 18
Visit (V)j	V1	V1.1 a			V3	V4				V5			V6			V7	V8 SFU	
Study day	{-21} or {-43}^b-D	{-21} D			1	8	15	22	29	43		70		91		112	126	
Visit measures	All Screening Procedures	UDysRS part 4			Safety		Safety		Safety		Safety		Safety		Safety		Safety	
		Concordance testin			Efficacy		Efficacy		Efficacy		Efficacy		Efficacy		Efficacy		Efficacy	
		3x24h "ON/OFF" home diaries			*UDysRS only				PR				PR		PR		PR	
Arms:		Placebo																
		75mg Q48h (75 mg every other day) 1 week				75mg QD (75 mg/day) 1 week	75mg BID (150 mg/day) 1 week	100 mg BID (200 mg/day) 1 week	100mg BID (200mg/day) 12 weeks								2 days 75 mg BID + 2 days 75 QD	

a Only for patients requiring an amantadine washout period

Abbreviations: BID, twice daily; PK, pharmacokinetic; Q48h, once every 48 hours, QD, once a day; SFU, safety follow-up; UDysRS, Unified Dyskinesia Rating Scale; V, visit; Wk, week

## 4.2 Study Treatment

Subjects who met eligibility criteria were randomly assigned at Baseline (Visit 2) to receive pridopidine 100 mg BID, 150 mg BID or placebo using a 1:1:1 randomization. No stratification factors were used in the randomization. During the 14/16-week active treatment period, two oral capsules were taken in the morning (at 7:00 AM  $\pm$ 1 hour) and 2 oral capsules in the afternoon (at 1:00 PM  $\pm$ 1 hour). The time difference between the 2 administrations was 6-8 hours apart.

Subjects in the active treatment arms underwent either a 2-week (original amendment) or a 4-week (Amendment 1) dosage titration period as described below:

- Original protocol: Subjects who underwent a 2-week titration period were treated for 3 days with pridopidine 75 mg QD (once daily), 4 days of pridopidine 75 mg BID, and 1 week with pridopidine 100 mg BID.
- Amendment 1: Subjects who underwent a 4-week titration period were treated with pridopidine 75 mg on alternate days (Q48h) during one week, 75 mg QD during 1 week, 75 mg BID during 1 week, and 100 mg BID during one week.

Under both protocol versions, maintenance treatment with pridopidine 100 mg BID or 150 mg BID was then continued for an additional 12 weeks.

Subjects randomly assigned to the placebo arm received matching placebo throughout the treatment period in a double-blind fashion at the same dosing schedule as subjects assigned to the active treatments.

At the end of the maintenance period or at early termination (ET), all subjects underwent a down-titration period in which they received 1 capsule of pridopidine 75 mg (or the matching placebo) and 1 capsule of

## Statistical Analysis Plan

placebo BID on Days 1 to 2 followed by one capsule of pridopidine 75 mg (or the matching placebo) and one capsule of placebo QD on Days 3 to 4 of Week 17.

### 4.3 Study Population

PD subjects with a documentation of mild to moderate LID (subjects with severe LID were included after Amendment 1) by the investigator and by home diary were enrolled in the study. The full list of inclusion criteria can be found in Section 4.1.1 of the study protocol and exclusion criteria in Section 4.1.2 of the study protocol.

## 5 Analysis Populations

The following analysis populations (analysis sets) will be used for the analysis of the disposition, demographic, efficacy, safety and PK data.

Subjects will be grouped according to the actual treatment received if there were inaccuracies in study drug taken compared to what treatment subjects were randomized to.

### 5.1 Efficacy Evaluable (EE) Population

The Efficacy Evaluable 1 (EE1) population includes all subjects that were randomized, received at least 80% of their dose of study drug and were on treatment at Visit 3 (Week 3/5) and have a post-randomization assessment of the primary endpoint.

The Efficacy Evaluable 2 (EE2) population includes all subjects who were on treatment at Visit 5 (Week 8/10), have at least 80% compliance to study drug and have a valid assessment of the primary endpoint.

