## Statistical Analysis Plan

All applicable data will be summarized by treatment group (pridopidine 150 mg BID, pridopidine 100 mg BID, pridopidine 150 mg BID and 100 mg BID pooled active or placebo). Where appropriate, data will be summarized by visit in addition to the treatment group.

Unless otherwise indicated unscheduled or repeat assessments will not be included in summary tables, but will be included in listings. For safety analyses which summarize the total number of abnormal values over the whole study or period, the unscheduled or repeat assessments will be used for these totals, but not for the visit-specific analyses. For assessments done at the ET visit, these assessments will be used as data for the scheduled visit closest to the ET time point, in case the corresponding data are missing from this closest visit.

Unless specific otherwise, baseline is defined as the last non-missing assessment prior to the first dose of the study drug.

Continuous variables will be summarized using the number of observations (n), mean, standard deviation (SD), first quartile (Q1), median, third quartile (Q3), minimum, and maximum. Standard error of the mean (SEM) will also be provided for summaries of efficacy data, if relevant.

Descriptive statistics for categorical data will include frequency counts and percentages. The total number of subjects in the treatment group overall (N) will be used as the denominator for percent calculations, unless stated otherwise. Missing categories will be included as appropriate.

Significance testing will be 2-sided using  $\alpha = 0.05$ , unless otherwise specified.

All statistical analyses and summaries will be produced using SAS version 9.4 or higher. Deviations from the statistical plan will be reported in the clinical study report, including the rationale for the deviation.

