### 9.2.2 Handling of Missing Longitudinal Data

The following methods will be used to manage longitudinal incomplete data after the data within each visit has been imputed as described above.

- For the primary efficacy analysis, likelihood-based modeling approach will be used to handle incomplete data. For this purpose, Mixed Model for Repeated Measures (MMRM) will be applied, see Section 14.1.
- Sensitivity analyses for the primary endpoint data will be conducted using the Multiple Imputation (MI) approach. For the MI approach, each missing value will be replaced with a set of plausible values that represent the uncertainty about the right value to impute, see Section 14.1. Imputation will only be done under the assumption of Missing At Random (MAR).

Safety data will not be subject to any imputation and will be summarized on an observed case basis.

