## 10 Subjects Disposition, Demographic and Other Baseline Characteristics

The following will be summarized in the Subject Disposition table.

- A summary of the number of subjects in each of the analysis populations.
- The number and percentage of subjects who were randomized but not treated.
- The count and percentage of subjects who completed or discontinued from the study or treatment. For those who discontinued from the study or treatment, the primary reason for discontinuation from the study or treatment will be presented.

Demographics and baseline characteristics will be summarized descriptively for the Safety Population, by treatment group and overall. For categorical endpoints, categories for missing data will be presented.

The following variables will be summarized:

- Demographics: age (continuous, calculated as date of informed consent minus date of birth, divided by 365.25), age categorized as <65 years versus  $\geq 65$  years, gender, ethnicity, race, height, weight, BMI (calculated as weight [kg] divided by squared height [ $m^2$ ]) and country. In case of missing day of birth, the day will be imputed as 15. In case of missing month of birth, the month will be imputed as 6.
- PD history: time since diagnosis of PD, time since start of levodopa treatment and time since onset of levodopa-induced dyskinesia, all measured in years at time of informed consent
- Report of direct observation of ON-time with dyskinesia during half-hour periods of the screening visit
- Baseline dyskinesia status: total score on UDysRS part 4 disability scale.
- Cognitive status: Mini-Mental State Examination (MMSE) total score (as categorical, % of subjects with a score of 30, 29, 28, 27, 26 or <26)
- Distribution of Modified Hoehn and Yahr stages
- Total daily levodopa dose (mg) and distribution of dosing frequency at Screening.

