### 14.1 Primary Endpoint

The primary endpoint of this study is the mean change from Baseline (Visit 2) to Visit 3 and Visit 5 in the sum of Parts 1, 3, and 4 of the UDysRS. The difference in the primary endpoint between the groups (pridopidine 150 mg BID versus placebo, pridopidine 100 mg BID versus placebo) will be estimated using a MMRM using the EE1 and EE2 populations after imputing missing data under assumption of MAR. The model will include the observed changes from Baseline using Visits 3, 4, 5, 6 and 7 as the response values. The treatment difference at each visit will be estimated using contrasts. The MMRM will include the treatment group (pridopidine 150 mg BID, pridopidine 100 mg BID or placebo), visit (3, 4, 5, 6 or 7) and the interaction between the treatment group and visit as fixed factors. The baseline value will be used as a covariate in the model.

A separate analysis will compare pooled active vs placebo under same assumptions as above.

An unstructured covariance structure will be applied for MMRM. In case the model will not converge with the unstructured covariance structure, heterogeneous Toeplitz structure (TOEPH), Autoregressive with heterogeneity (ARH (1)), Heterogeneous variances with Compound Symmetry (CSH), Toeplitz (TOEP), Autoregressive(1) (AR(1)) or Compound Symmetry without heterogeneous variances (CS) covariance structure will be used instead in this order. The denominator degrees of freedom will be computed using the Kenward-Roger method.

The least square (LS) means, standard errors and LS mean differences between pridopidine 150 mg BID versus placebo and pridopidine 100 mg BID versus placebo at each visit along with the 95% confidence intervals (CIs) will be provided. The nominal p-values for the hypothesis testing will also be provided. Treatment difference will be assessed with a 2-sided alpha level of 0.05.

The EE1 and EE2 populations will be used for the primary efficacy analysis.

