## 14.2 Secondary Endpoints

### 14.2.1 Continuous Secondary Endpoints

The secondary endpoints that will be treated as continuous (all endpoints derived from “ON/OFF” home diaries, UDysRS questionnaire and UPDRS questionnaire part 2 and 3) will be analyzed with MMRMs similar to the one used for the primary endpoint. The baseline value of the analysis variable in question will be used as the baseline covariate in the MMRM. The analyses will be performed in the EE1 and EE2 set. In addition to Visit 7, data from Visits 3, 4, 5 and 6 will be analyzed as well.

For “ON/OFF” home diaries, in addition to the secondary endpoints, also ON time with troublesome dyskinesia and ON time with ON time with non-troublesome dyskinesia will be analyzed as well.

For UDysRS, all four sum scores (Part 1, Part 2, Part 3 and Part 4), Individual parts.

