### 15.2 Compliance

Subjects will be instructed to bring with them the used and unused drug kits at Visit 3, Visit 5, Visit 6, Visit 7/ET, and at Visit 8/FU, in which treatment compliance will be evaluated. Treatment compliance at the Visit 3, Visit 5, Visit 6, Visit 7/ET, and Visit 8/FU and overall for the 14 week active treatment period will be calculated using the following formula:

$$\text{Compliance (\%)} = [\text{Total number of administered doses} / \text{Total number of scheduled doses}] \times 100$$

The total number of scheduled doses will be calculated based on the extent (days) of exposure of each subject. A range between 80% to 120% will be taken as reference limits for a satisfactory level of compliance. The compliance (expressed as %) will be summarized with descriptive statistics by treatment group. In addition, the number (and %) of subjects with compliance between 80% to 120% will be tabulated by treatment group.

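### Every SAP efficacy analysis that names a set selects on post-randomisation compliance and treatment status, and no as-randomised analysis is left beside it

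*SAP*

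**What the plan says.** SAP 5 defines four sets: EE1, EE2, Safety and PK.

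- EE1 needs randomisation, at least 80% of dose, being on treatment at Visit 3 and a post-randomisation primary assessment.
- EE2 "includes all subjects who were on treatment at Visit 5 (Week 8/10), have at least 80% compliance to study drug", with a valid primary assessment.
- On grouping, SAP 5 says: "Subjects will be grouped according to the actual treatment received if there were inaccuracies in study drug taken".
- For the primary endpoint (SAP 14.1): "The EE1 and EE2 populations will be used for the primary efficacy analysis". For the continuous secondary endpoints (SAP 14.2.1): "The analyses will be performed in the EE1 and EE2 set".
- SAP 9.2.2 confines imputation to a missing-at-random (MAR) assumption.

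Protocol 7.7 and 7.9.1 planned something else. The primary MMRM was to be in the mITT set, grouped as randomised. Sensitivity analyses were multiple imputation in the ITT set (MAR and copy-reference), a completer-set MMRM, and an analysis adding assessments made after treatment was stopped. SAP 2 and SAP 17 state that the SAP takes precedence. SAP 17 is a single sentence that neither lists nor justifies the analyses dropped.

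**The concern.** Staying on pridopidine with good compliance need not select the same kind of patient as staying on placebo. Both EE sets condition on events after randomisation, so they do not keep the comparability that randomisation gave. The exposed period is titration, which lies wholly before Visit 3. Protocol 5.3.1 discontinues patients who still cannot tolerate treatment after one dose reduction, and SAP 4 records that titration was lengthened from 2 to 4 weeks through an urgent safety letter. The documents give no discontinuation counts. SAP 3.1 makes Visit 3 part of the primary objective, so losses in this period bear directly on a primary result, and no planned efficacy analysis would show their effect.

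**Working it through.** **1. Which set each efficacy analysis uses**

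| Endpoint | SAP section | Set |
|---|---|---|
| Primary UDysRS sum | 14.1 | EE1, EE2 |
| Diary endpoints | 6.2.2 heading line, 14.2.1 | EE1, EE2 |
| UDysRS total | 6.2.2, 14.2.1 | EE1, EE2 |
| UPDRS Parts 2 and 3 | 6.2.3, 6.2.5, 14.2.1 | EE1, EE2 |
| Responders | 6.2.4 | EE1, EE2 |
| PGI-C, CGI-C | 6.2.6 | EE1 |

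**2. What happens to each kind of patient**

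- Stops before Visit 3 and does not resume: fails EE1 and EE2, so is in no efficacy analysis.
- Poor compliance before Visit 3 but continues: out of EE1 if the 80% rule is applied at Visit 3, but can enter EE2. Neither rule states a time window, and EE2 does not require EE1 membership.
- Stops between Visits 3 and 5: can stay in EE1, with later visits handled under MAR; out of EE2.

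The imputation of a missing Visit 3 value (SAP 14.1) and the responder analysis that counts missing as non-improvement (SAP 6.2.4) both operate inside EE1 and EE2. Neither brings an excluded patient back.

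**3. The plan's own figure**

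Difference 8.5, SD 13, two-sided 0.05, two-sample t-test: power is 0.792 at 37 per arm and 0.803 at 38, so 38 reproduces. With 15% drop-out, 38/0.85 = 44.7, rounded up to 45 per arm, or 135. SAP 9.3 says fewer than 30 were enrolled. At 9 or 10 per arm, power for 8.5 points is 0.257 or 0.283 before any exclusion.

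**4. Possible bias in EE1 at Visit 3**

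Assumed, because the documents give no exclusion rates: no true effect; SD 13 (the planning value); 9 per arm; the worst 1 of 9 removed from each active arm and none from placebo; correlation r between the selection variable and the outcome.

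The expected largest of 9 standard normals is 1.485. Removing it shifts the mean of the other 8 by -1.485/8 = -0.186 SD of the selection variable. Bias = 13 × r × (-0.186); a negative value favours pridopidine.

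Standard errors: one dose vs placebo, 13 × √(1/8 + 1/9) = 6.32; pooled active vs placebo, 13 × √(1/16 + 1/9) = 5.42.

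The bias column comes from the formula. The other columns come from 200,000 simulated trials per case, in which the bias was -0.71, -1.20 and -1.71 for one dose and -0.71, -1.21 and -1.71 for pooled active.

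| r | Bias (points) | One dose: bias/SE, type I error | Pooled: bias/SE, type I error |
|---|---|---|---|
| 0.3 | -0.72 | 0.11, 0.052 | 0.13, 0.053 |
| 0.5 | -1.21 | 0.19, 0.056 | 0.22, 0.059 |
| 0.7 | -1.69 | 0.27, 0.062 | 0.32, 0.068 |

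If placebo also loses its worst 1, the bias is 0. If only placebo does, it is +0.70 to +1.70.

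A cruder check multiplies the excluded fraction by the gap between kept and excluded patients. One of 9 with assumed gaps of 4.25, 8.5 and 13 points gives 0.47, 0.94 and 1.44 points, which is the same order.

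EE2 read alone is more exposed. Removing the worst 2 of 9 from one side only at r = 0.7 (second order statistic 0.932) gives 13 × 0.7 × (1.485 + 0.932)/7 = 3.14 points in either direction. That is an extreme case, and EE1 keeps patients who stop after Visit 3.

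**The case against.** The strongest reply is that an on-treatment question is reasonable here. SAP 4 recasts the trial as a terminated proof-of-concept study, SAP 9.4 treats p-values as mainly descriptive, and sampling error is far larger than the bias above. Exclusions are also partly visible. SAP 10 promises "A summary of the number of subjects in each of the analysis populations" and the discontinuation reasons; SAP 15.2 says "subjects with compliance between 80% to 120% will be tabulated by treatment group"; and SAP 9 lists all subject data, so fewer than 30 patients can be traced one by one. All of this stands and keeps the stakes small. It does not explain why no as-randomised result is reported alongside, which needs no larger sample, and no planned table shows EE exclusions by randomised arm and reason.

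The protocol's mITT set is not full ITT either: it requires a post-randomisation efficacy assessment. Imputation models in so few patients may be unstable. Both points stand and shape the fix.

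A reader might infer three stronger points that the documents do not support.

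- *All early non-compliance is lost.* Only stopping before Visit 3 without resuming is firmly excluded.
- *Restoring mITT fails because early-termination (ET) scores are discarded, and moving them to Visit 3 removes the bias.* Where the nearest visit's data are missing, SAP 9 says of ET assessments that "these assessments will be used as data for the scheduled visit closest to the ET time point". Read literally, with Visit 3 on Day 29, ET scores on Days 2 to 14 (13 of 27 days, plus a tie on Day 15) are nearest to the already-filled Baseline. But SAP 9 also defines baseline as before the first dose, so the rule can fairly be read as covering post-baseline visits only. The share at risk also depends on timing. Protocol Table 4, footnote c, allows the ET visit up to a week after stopping; if stopping days are even over Days 2 to 28 and the visit is 7 days later, only 7 of 27 fall on or before Day 15. A score taken during titration is a stand-in for Visit 3, so complete removal of bias cannot be claimed.
- *The plan favours pridopidine.* The sign depends on which arm loses which patients.

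**Conclusion.** The point holds as a cheap improvement with small stakes. The SAP conditions every efficacy analysis that names a set on compliance and treatment status after randomisation, and it keeps none of the protocol's as-randomised or not-missing-at-random analyses. Early termination and small numbers lessen the consequence but do not justify the omission. The EE1 figures, to be read against a planning effect of 8.5 points, rest on assumed exclusions, an assumed correlation and 9 per arm, which is close to the upper bound on enrolment. Exclusions that are equal across arms, or due only to study termination, may do no harm.

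**What to change.** Before database lock, while the study is still blinded (SAP 2):

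1. Define the protocol's mITT set in SAP 5, grouped as randomised. Report the SAP 14.1 primary MMRM in it beside EE1 and EE2, and label those two as on-treatment analyses. mITT tables for the secondary endpoints are optional.
2. As sensitivity analysis of the primary endpoint, add off-treatment assessments where they exist. Protocol 4.2 encourages patients to continue visits after stopping, so there may be some. Run the protocol's ITT imputation (MAR and copy-reference) only if the models are stable with fewer than 30 patients.
3. State in SAP 9 that an ET UDysRS taken after the first dose maps to a post-baseline visit and never to Baseline. This settles an ambiguity; it is not claimed to remove the bias.
4. Add to the SAP 10 disposition table the number excluded from EE1 and from EE2, by randomised arm and reason (adverse event, lack of benefit, study termination, compliance below 80%, no valid UDysRS).

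The cost is SAP wording and a few extra tables, with no new data collection. The downsides are a possibly diluted estimate and imprecise sensitivity results. Patients with no post-baseline assessment remain outside mITT and are covered only if the ITT imputation is run.
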